Technology-based brief assessments and prevention programs can revolutionize healthcare by allowing for low-cost, easily accessible, low-burden, effective prevention in healthcare settings without taking away from routine healthcare provided by physicians. It is essential that interventions target multiple health behaviors. This intervention focuses on several high-risk health behaviors among adolescents including substance use, SA, and SRBs, all of which are associated with both physical and mental health problems. This patient-oriented career development award would allow the candidate to pursue this line of research and ultimately develop, test, and disseminate effective technology-based prevention programs related to substance use, SA, and SRBs within primary care settings.

B. Developing an intervention for use by real-world providers. Adolescents prefer to be asked questions regarding substance use using technology-based or pencil paper modalities compared to physician-led assessments⁴⁸. Therefore, the development of a technology-based brief assessment and intervention would be an innovative method to provide services to patients with minimal added burden to providers. Further, this brief assessment and intervention will be informed by both providers and patients in community-based primary care settings, allowing for the specific needs of real-world providers to be addressed in the development of the intervention, thereby increasing the likelihood of dissemination and implementation ease.

C. Informing best practices for implementing assessment and prevention programs targeting SA and SRB in primary care settings. There is limited information in the assessment and prevention of SA and SRB among adolescents in primary care. The proposed research will not only provide feasibility and effect sizes for a future RCT to examine this intervention, it will also result in guidelines to implement substance-involved SA and SRBs within primary care settings guided by patient and provider preferences which could also inform other sensitive topics useful to assess in primary care settings.

4-2. Research Aims

A. Pilot Feasibility Trial

Participants: A total of 250 adolescents aged 14-18 will be recruited for a pilot feasibility trial. Adolescents will be screened using a screening assessment to determine if they are eligible for the study based on inclusion and exclusion criteria described below.

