Method: After their Well Check Visit with their pediatrician, adolescents will be recruited virtually or in-person to complete a screening survey about substance use. Participants who are ineligible to complete the study because they did not use substances or have friends that use substances in the past year will receive the recommended reinforcing message for abstaining from substance use such as “You’ve made a smart decision not to use alcohol or drugs” to reinforce choice (adapted from the Alcohol Screening and Brief Intervention for Youth⁶³). This “screening out” procedure will allow for adolescent substance non-use to be reinforced in the recommended manner to save time for providers by providing evidence-based care. Eligible participants (and their guardian) will be invited to meet with a research assistant either in person at the clinic, by phone, or in

a video conference meeting to discuss the research and obtain consent. While discussing informed consent, participants and their guardians will be informed of the sensitive nature of the prevention program and that the adolescent will complete the brief survey and then research procedures. Both the adolescent and guardian will be informed that if the adolescent discloses a SA history as a child that has not been previously reported to the appropriate officials (Department of Social Services or Law Enforcement depending on the perpetrator), a report will need to be made prior to the adolescent and guardian leaving the clinic. Both the adolescent and guardian will be informed that if the adolescent discloses imminent risk of suicide and the adolescent is not willing to agree to a safety plan, a mental health professional will need to conduct an exam to determine if hospitalization is needed.

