After consenting to the prevention program and completing the baseline survey, the adolescent will be randomized to receive the interactive online prevention program (15 minutes) or no intervention. All participants will then be contacted to complete 1-, 3-, and 6-month follow-up assessments. Participants will receive a \$5 gift card for screening for the study, \$30 gift card for completing the baseline survey up to the point of randomization (plus \$10 for completing the intervention if randomized to that condition), \$40 gift card for the 1-month follow-up, \$45 gift card for the 3-month, and \$50 gift card for the 6-month. Participants may also receive partial payment for the follow-up surveys based on the percentage of the survey they complete. They will also receive a \$5 bonus for completing each survey within a week of the date it was sent, and a \$10 bonus if they complete all the surveys. Additionally, participants randomized to the intervention group will receive an additional \$10.

The research team will observe restrictions imposed by Georgia State University and relevant government or public health authorities in the conduct of research activities.

5. Study Design

A. Organizational

The Principal Investigator of the overall study is [name] and is housed at Georgia State University (GSU). This study is funded by a NIDA career development award to GSU and all funds will go through GSU.

B. Setting and location:

Study procedures will take place at GSU and recruitment will occur at two sites: in the Old Fourth Ward Pediatrics clinic in Atlanta, Georgia and at the Medical College of Georgia-Augusta University Children's Hospital of Georgia in Augusta, Georgia.

Adolescents will either complete the consent, baseline survey, and intervention at their primary care clinic or they will complete those study activities online in a private location of their choosing. All participants will complete the follow-up surveys at 1 month, 3 months, and 6 months online in a private location of their choosing. When completing data surveys and/or the intervention remotely, we will ensure that they are in a private space in these ways:

- 1) displaying a reminder screen at the beginning of all surveys and the intervention that this should be completed in a private location
- 2) displaying a reminder screen to close the browser at the end

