Feasibility will be determined based on recruitment, retention, execution of study protocols, and satisfaction of adolescents and providers. Feasibility is the primary goal of this aim. Recruitment will be considered successful if 250 adolescents are screened and 70 meet criteria for the study. Study retention will be considered successful if 80% of participants are retained for 1-, 3-, and 6-month follow-up assessments. Satisfaction will be considered adequate if participants report at least average satisfaction with the prevention program. Feasibility will be used to inform a larger randomized clinical trial. Preliminary effects: Preliminary effects will be examined as a secondary goal to determine preliminary evidence of effects on substance use, SA victimization, SA perpetration, and SRBs. The small sample size prevents any conclusions regarding prevention program efficacy to be determined, however, ANOVAs (gender X treatment

condition) will be conducted to determine if there are any preliminary effects on substance use, SA victimization, SA perpetration, and SRBs. Given that the primary aim is to determine feasibility and not to determine effects on outcomes, this will be preliminarily examined.

11. Training of Study Team

All study staff will be approved by all involved IRBs and will receive extensive training from the grant PI ([name]) on study procedures and risk protocols. Specifically, study staff will receive training on suicide risk assessment and suicide risk management as well as on assessing for child safety in relation to sexual assault histories. All investigators and study staff will complete the required CITI training and study staff with direct contact with participants will have weekly supervision meetings as well as 24-7 access to [name], a licensed clinical psychologist, for any study-related concerns.

12. Plans for Monitoring the Study for Safety

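### Must the 80% retention criterion say whether it applies at each visit or to all three visits together?

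*Combined protocol and SAP*

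**What the plan says.** Section 10 (Plans for Analysis, Statistical and/or Otherwise) makes feasibility the primary goal and judges it on recruitment, retention, execution of the protocol and satisfaction. The retention rule is one sentence: "Study retention will be considered successful if 80% of participants are retained for 1-, 3-, and 6-month follow-up assessments". The recruitment rule beside it reads "Recruitment will be considered successful if 250 adolescents are screened and 70 meet criteria for the study", and the stated use of the results is that "Feasibility will be used to inform a larger randomized clinical trial". No rule combines the four components, and no go/no-go decision is tied to any one of them.

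Three other places bear on the reading:

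- Section 4-2 (Research Aims, Method) puts consent and the baseline survey first, then randomisation, and then states: "All participants will then be contacted to complete 1-, 3-, and 6-month follow-up assessments". Section 5F likewise gives the follow-up surveys to eligible, consented adolescents after the baseline procedures.
- Sections 4-2 and 8 pay a set amount for each follow-up survey and a separate "bonus if they complete all the surveys". They also provide that "Participants may also receive partial payment for the follow-up surveys based on the percentage of the survey they complete".
- Section 4-2 (Participants) states "A total of 250 adolescents aged 14-18 will be recruited for a pilot feasibility trial", whereas Section 10 uses 250 for those screened. Section 4-2 (Method) also applies the word to screened-out adolescents: "Participants who are ineligible to complete the study because they did not use substances".

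**The concern.** A numerical success threshold for part of the primary goal should have one meaning before the data are seen. This sentence leaves room for more than one.

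- **Visits.** It can mean 80% at each visit or 80% completing the full series. Everyone is contacted at every time point, so a participant can miss month 3 and return at month 6. Such a participant counts at two visits but not among those completing all three.
- **Denominator.** The number to be randomised is not given, 250 is used in two ways, and the word for participants is used loosely.
- **Partial surveys.** They are foreseen and paid for, but nothing says whether they count as retained.

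If the reading were picked afterwards, the sponsor could report the one that passes. The larger trial might then be planned on too favourable a view of follow-up.

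**Working it through.** The 80% is a chosen threshold without a derivation, so there is no figure to reproduce. The check is whether the readings give different verdicts, and when.

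**Inputs.** From the documents: the 80% threshold, three visits, and 70 adolescents meeting criteria (Section 10). Assumed, because the documents give none: that 70 are randomised, the true retention per visit, and the correlation of attendance within a person. The pass mark is 0.80 × 70 = 56.

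**Relation of the two readings.** Anyone who completes all three visits is counted at every visit. A pass on all three is therefore always a pass at each visit, and disagreement runs one way only. If dropout is monotone, the all-three completers are exactly the month-6 completers and the verdicts coincide. With all 70 present at month 1, all-three completers = month-6 completers minus those who missed month 3 and returned.

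**Example.** Of 70, five miss only month 3, five leave after month 1 and five leave after month 3.

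- Month 1: 70/70 = 100%
- Month 3: (70 − 5 − 5)/70 = 60/70 = 86%
- Month 6: (70 − 5 − 5)/70 = 60/70 = 86%
- All three: (60 − 5)/70 = 55/70 = 79%

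The rule passes at each visit and fails on all three.

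**How often the verdicts differ.** Take a beta-binomial model with per-visit rate m and within-person correlation ρ. Put s = 1/ρ − 1 and a = m·s. The all-three rate is m × (a+1)/(s+1) × (a+2)/(s+2). For m = 0.85 and ρ = 0.7, s = 0.429 and a = 0.364, so the rate is 0.85 × 0.955 × 0.974 = 0.790. The exact binomial chance of at least 56 of 70 is then 49%. Each-visit figures at 85% are simulated.

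| True rate per visit, N = 70 | ρ | Pass at each visit | Pass on all three |
|---|---|---|---|
| 85% | 0 | 74% | 0.1% |
| 85% | 0.5 | 79% | 19% |
| 85% | 0.7 | 82% | 49% |
| 85% | 0.9 | 86% | 80% |
| 90% | 0.7 | about 99% | 93% |

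In the last row, the all-three rate is 0.90 × 0.970 × 0.982 = 0.858. The each-visit figure follows from a single-visit pass chance of 0.9965: 0.9965³ = 0.990 if visits are independent. A separate simulation with correlated visits gave much the same.

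Because disagreement runs one way, its probability is the difference between the two columns. It is large when the true rate is close to the threshold and people come and go freely. It is about 6 points when attendance is strongly clustered within persons (86 − 80) or when retention is 90% with ρ = 0.7 (99 − 93).

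**Denominator.** Suppose 70 meet criteria, 66 are randomised and 54 are retained (assumed counts). Then 54/70 = 77% and 54/66 = 82%. The four who were never randomised were never sent a follow-up survey, so they are a loss at enrolment. Under the sequence in Sections 4-2 and 5F, the adolescents who can be retained are those randomised.

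**Partial surveys.** With 53 full completers, 53/70 = 76%; counting three partial surveys gives 56/70 = 80%. The threshold can flip here too, but only within a few participants of it.

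**Precision.** An observed 56/70 has an exact 95% interval of 69% to 89%. A result this close to 80% says little about which side of it the true rate lies, under any reading.

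**The case for a change.** The strongest case for a change is that the sponsor itself attached a number to its primary goal. A threshold with two readings is not fully pre-specified, and one sentence would settle it. Reporting both proportions later would be open, but it would not say which one decides. That the study is a pilot does not remove the ambiguity. The effect can also be large: at 85% per visit with correlation 0.5, the rule passes 79% of the time on one reading and 19% on the other.

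Part of this stands. The sentence is ambiguous, no other section resolves it, and a stated reading would be tidier. The partial-survey point also survives as a small gap, because payment terms do not define retention.

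The rest does not carry the case. The denominator is settled well enough by the order of procedures. The mismatch over 250 concerns recruitment numbers, not who is counted as retained. The large differences need a true rate near the threshold and frequent return after a missed visit, and the documents give no ground for expecting either. Nothing in the plan makes a later decision turn on the retention verdict alone. Whoever designs the larger trial will need the observed proportions, and the pilot supplies both whichever label is attached to them.

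**Conclusion.** No change to the plan follows. The criterion omits a definition, but either reading gives a valid descriptive answer. Both are computed from the same follow-up records, and an analyst would ordinarily show completion by visit together with the number completing every visit. A reader can then apply the stricter reading.

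The two visit readings agree fully under monotone dropout and can disagree when participants miss a visit and return. In the 70-person example, five returners separate 86% at the lowest visit from 79% overall. That count, the retention rates and the correlations are assumptions used to show the range. The conclusion does not depend on their exact values. It rests on retention being one of four components of a pilot's feasibility assessment, on there being no inferential claim or single decision attached to it, and on the randomised group being the natural denominator.

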Ongoing monitoring of SA victimization will be conducted throughout the duration of the study using self-report measures. As described above, any youth or caregiver reports of harm to the child will be made to the local division of the Department of Social Services and/or law enforcement agency, when necessary. In the event that there is evidence (by

child/guardian report or physical evidence) that the child would be in danger of physical harm upon returning to the home, the appropriate law enforcement agency will be called and the child will not be permitted to leave with the guardian (i.e., if the abuser lives in the home).

[name] is well-versed in mandating reporting and will be available on an as needed on-call basis during the duration of the study to pediatricians who may have any questions regarding study policies. Mandatory reporting within the study, combined with discussion of other sensitive topics including substance use may bring up questions from pediatricians regarding best practices concerning adolescent substance use, SA, and SRBs. Therefore, [name] will be available on call.

To minimize distress or discomfort associated with participation in the study (from either assessment or the prevention program): (a) research staff will be carefully chosen and highly trained by the P.I.; (b) participants will be informed that they can discontinue participation at any time; and (c) if other problems arise, the research personnel or a licensed psychologist will contact the family to address and resolve these issues. To ensure this is possible, the research personnel and/or a licensed psychologist will be available during recruitment procedures at all times virtually.

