attempts, are possible given the high-risk nature of the population under study. Regardless, both expected adverse events and unexpected adverse events will be monitored and addressed continuously throughout the course of the project. Risk of harm to self and others will be directly assessed through self-report questionnaires. Participants in the study who indicate any risk of harm will immediately be assessed and referred for treatment, if needed. [name] and her mentorship team have extensive training in crisis management. [name] was directly clinically trained by [name], the developer of Dialectical Behavior Therapy which is effective at reducing suicidal behavior. Therefore, she is well versed and very experienced in the assessment and management of acutely suicidal individuals. Both expected and unanticipated adverse events will also be continuously monitored by the candidate and mentorship team. All study staff will be closely supervised by the candidate, who will hold weekly meetings with the staff to address clinical barriers, prevention program and enrollment progress, and safety issues throughout the feasibility trial. [name] will also be available 24/7 to study staff by phone if any additional support is needed. Participant safety is assessed routinely as part of the research context through assessments given at each time point to evaluate substance use, SA, SRBs, and risk of harm.

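### Section 10 gives the pre-randomisation baseline values no role in the preliminary-effects ANOVAs; adding them as a covariate is a cheap, low-priority gain in precision where baseline predicts the outcome at least moderately

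*Combined protocol and SAP*

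**What the plan says.** The effect analysis is one sentence in section 10: "The small sample size prevents any conclusions regarding prevention program efficacy to be determined, however, ANOVAs (gender X treatment". The outcomes it goes on to list are four: use of substances, being a victim of sexual assault, perpetrating it, and sexual risk behaviours. Two factors are named, gender and condition. The section names no covariate, change score, time factor or analysis visit, and no other section gives baseline values a part in estimating effects. Section 10 then limits the weight of the exercise: "Given that the primary aim is to determine feasibility and not to determine effects on outcomes, this will be preliminarily examined".

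The data for an adjusted analysis are already planned. Section 4-2 (Method) places the baseline survey before allocation: "After consenting to the prevention program and completing the baseline survey, the adolescent will be randomized to receive the interactive online prevention program". On follow-up it says: "All participants will then be contacted to complete 1-, 3-, and 6-month follow-up assessments". Section 12.A refers to "assessments given at each time point to evaluate substance use, SA, SRBs, and risk of harm", and section 6 adds: "Ongoing monitoring of SA victimization will be conducted throughout the duration of the study using self-report measures".

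Section 4-1, item C, gives the effect sizes a purpose: the research will "provide feasibility and effect sizes for a future RCT to examine this intervention".

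**The concern.** A baseline value measured before randomisation cannot be affected by the arm. Where it predicts the follow-up value, using it as a covariate removes outcome variance that has nothing to do with treatment and narrows the interval around the treatment difference. The two-factor ANOVA, as worded, leaves that variance in.

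What is at stake is modest. Nothing in the feasibility criteria depends on it. But a later trial planned from these effect sizes inherits their uncertainty, and with a few dozen participants per arm that uncertainty is large. Reducing it with data already being collected serves the protocol's own aim.

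**Working it through.** The documents give no power, SD, correlation or target precision, so there is no stated figure to reproduce. The calculation below is illustrative.

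**Inputs from the protocol.** 70 meeting criteria and 80% retention (section 10): 0.80 × 70 = 56 analysed. Two arms and three follow-ups (section 4-2).

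**Assumptions.** All 70 eligible adolescents consent and are randomised; 1:1 allocation, so 28 per arm; equal gender split; outcome roughly continuous with SD 1; baseline-outcome correlation r of 0.1, 0.3, 0.5 or 0.7. For the three-visit mean, also complete data and the same r between all visits.

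**Reference: planned ANOVA at one visit.** The standard error of the treatment difference is √(2/28) = 0.267. With 56 − 4 = 52 degrees of freedom the 95% half-width is 2.007 × 0.267 = 0.54 SD.

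**Baseline added, one visit.** The variance factor is (1 − r²) × (1 + 1/50), where the second term is the cost of estimating the slope.

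**Mean of three visits.** The variance factor is (1 + 2r)/3 without baseline and [(1 + 2r)/3 − r²] × (1 + 1/50) with it.

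| r | One visit: variance factor with baseline | One visit: half-width without → with | Three-visit mean: half-width without → with |
|---|---|---|---|
| 0.1 | 1.010 | 0.54 → 0.54 | 0.34 → 0.34 |
| 0.3 | 0.928 | 0.54 → 0.52 | 0.39 → 0.36 |
| 0.5 | 0.765 | 0.54 → 0.47 | 0.44 → 0.35 |
| 0.7 | 0.520 | 0.54 → 0.39 | 0.48 → 0.30 |

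A simulation of the gender by condition model with 56 participants (6,000 replicates per scenario) gave single-visit variance ratios of 1.00, 0.95, 0.78 and 0.51, in line with the formula.

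**Break-even.** Setting (1 − r²) × 1.02 = 1 gives r² = 1 − 1/1.02 = 0.0196, so r is about 0.14. Below that, adjustment costs a little: variance is about 1% higher at r = 0.1 and 2% higher at r = 0.

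**Change scores.** An ANOVA on change from baseline would also fit the wording and would use baseline. Its variance factor is 2(1 − r), giving half-widths of 0.72, 0.63, 0.54 and 0.42 SD. These are wider than covariate adjustment at every r shown.

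**Larger sample.** Section 4-2 speaks of 250 recruited, while section 10 speaks of 250 screened. If 250 were randomised and 80% retained (100 per arm), the single-visit half-width would be 0.28 SD without baseline and 0.28, 0.27, 0.24 and 0.20 SD with it. The relative gain is nearly the same.

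**Rare outcomes.** With 28 per arm, the chance that at least one arm has no events at a visit is 1 − [1 − (1 − p)²⁸]². That is 81%, 42% and 10% at assumed prevalences p of 2%, 5% and 10%. A covariate model has little to work with there.

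**The case against.** The strongest reply is that this is a feasibility pilot. The effects are secondary, section 10 disclaims efficacy conclusions, and no decision rule depends on interval width. That stands, and it is why the point is a low-priority improvement and not a fault in the plan.

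It is also fair that the gain is not shown for every outcome. Two of the four concern sexual assault and may be rare. Substance use may be weakly predicted by baseline in adolescents who qualify through friends' use alone (section 5.D). The surveys are not reproduced, so it cannot be confirmed that baseline and follow-up recall windows match. A baseline measure of perpetration is inferred from the general reference to sexual assault in section 12.A. The recommendation therefore covers only outcomes with a matching baseline measure.

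A reader might infer several stronger things that the documents do not support:

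- **That the planned ANOVA is biased or invalid.** Randomisation makes it valid; the issue is precision only.
- **That any correlation with baseline brings a gain.** With 28 per arm there is none below about 0.14.
- **That baseline adjustment takes the half-width from 0.54 SD to 0.36, 0.35 or 0.30 SD.** Much of that fall comes from changing the target from one visit to the mean of three. The plan does not say how visits enter; a repeated-measures ANOVA would already capture part of it. The fair comparator is the unadjusted three-visit mean.
- **That the gender by condition term should be demoted.** Nothing here argues against it.

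**Conclusion.** The point holds as a cheap, low-severity improvement. Section 10 leaves out baseline values that are collected before randomisation and that would sharpen the promised effect sizes where they predict the outcome at least moderately. Under the stated assumptions with 28 per arm, the single-visit interval is about 4%, 13% and 28% narrower at correlations of 0.3, 0.5 and 0.7. For a three-visit mean, like for like, it is about 8%, 20% and 37% narrower. At 0.1 there is essentially no difference. The correlations, SD, allocation ratio and full enrolment of those eligible are assumptions, so the direction is firmer than the size. The feasibility conclusions do not change.

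**What to change.** Amend section 10 before outcome data are examined:

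- For each outcome with a matching baseline measure, add that baseline value as a covariate to the planned gender by condition model, keeping the gender term as planned.
- Name the follow-up contrast in advance: either one visit, or the mean of the 1-, 3- and 6-month values.
- Report the treatment difference for that contrast with a 95% CI.
- For rare sexual assault outcomes, report the proportion in each arm with exact intervals.

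The cost is a few sentences of text and slightly more analysis work, with no new data collection. The downside is about 1–2% higher variance for any outcome that baseline hardly predicts.

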Our proposed methodology was developed in order to balance the safety of human subjects with the ability to acquire accurate data. We have used similar procedures in both local and national studies. We ultimately chose a tablet-based intervention because individuals are more likely to disclose information about sensitive topics like sexual assault, alcohol use, and sexual risk behaviors in self-report measures than when asked by a person. Therefore, including the tablet-based intervention rather than an in-person intervention will increase the likelihood of disclosures. However, this is balanced with the human subjects concern and ethical concern of mandatory reporting laws. It is essential to ensure that children are safe from child abuse, and sexual assault is a form of sexual abuse. We have included mandatory reporting within these procedures to ensure that participants within this study are protected from future harm. However, it is notable that in the National Survey on Adolescents, which several of the mentors on the current project oversaw the Child in Danger protocol, out of the approximately 3600 youth confidentiality was broken in less than 5 cases total. Previous and current studies conducted by the research team have revealed that adolescents do in fact still disclose sexual assaults even with being informed that it is mandatory that we report the incident. However, it is possible that some adolescents will not disclose sexual assault if they are informed in will be reported to the authorities if disclosed. Because of this, we ensured that all participants will receive the same information and resources despite their reported histories to ensure that they receive the best care possible. It is a potential limitation that the sexual assault victimization experiences will likely be under representative of the actual rates in the population being observed.

Similarly, if an adolescent is threatening to hurt her/himself or someone else, confidentiality may have to be broken to make a report to the guardian and/or necessary authorities. Given that suicidality is common among child sexual abuse victims, while not a direct risk of the study, it is an important issue to assess and monitor closely with participants. Procedures for assessing and addressing suicide attempts are addressed in the following Protection Against Risk section.

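### Does using ANOVA for the two sexual assault outcomes leave the plan without a usable result when few or no events are reported?

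*Combined protocol and SAP*

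**What the plan says.** Section 10 makes feasibility the primary goal and preliminary effects a secondary one. It states that the sample is too small for any conclusion about efficacy. It then names two-way ANOVAs with gender and treatment arm as factors; the sentence ends "condition) will be conducted to determine if there are any preliminary effects on substance use, SA victimization, SA perpetration, and SRBs". No separate method, visit or scoring rule is given for the two SA outcomes. Section 5.F refers to follow-up surveys kept as separate documents, where the scoring may be defined.

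Section 4-1 C sets out what the pilot should deliver: "The proposed research will not only provide feasibility and effect sizes for a future RCT to examine this intervention".

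The sample size can be read in two ways. Section 4-2 A says "A total of 250 adolescents aged 14-18 will be recruited for a pilot feasibility trial", while Section 10 says "Recruitment will be considered successful if 250 adolescents are screened and 70 meet criteria for the study". On follow-up, Section 10 says "Study retention will be considered successful if 80% of participants are retained for 1-, 3-, and 6-month follow-up assessments".

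No SA rate during follow-up is given. Section 6 expects that, because disclosures must be reported to the authorities, "the sexual assault victimization experiences will likely be under representative of the actual rates in the population being observed". Section 12 A says SA is covered by "assessments given at each time point to evaluate substance use, SA, SRBs, and risk of harm".

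**The concern.** ANOVA compares means, and any SA during six months of follow-up may be a rare yes/no event. If no participant reports one, every sum of squares is zero and neither the F test nor its interval exists. Section 6 makes low reported numbers plausible. The pilot is meant to supply effect sizes, so a trial in which the only named analysis of two of its four outcome domains cannot be computed would seem to fail that purpose. Event counts by arm and a score-based risk difference can be reported whatever happens, so they look like the better choice.

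**Working it through.** **Inputs.** From Section 10: 70 eligible and 80% retained, so 70 × 0.8 = 56 followed. On the larger reading of Section 4-2 A: 250 × 0.8 = 200. Assumed, because the documents are silent: 1:1 allocation and equal genders (28 per arm, 14 per cell), all 70 randomized, any/none scoring, the same rate p in every cell, two-sided 5% tests. The plan has no power or precision figure to reproduce.

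**When F fails.** With no event, F = 0/0. With one event, each effect has sum of squares 56 × (1/56)² = 0.0179. The residual mean square is (1 − 1/14)/52 = 0.0179, so F = 1.00 and p = 0.32 whichever arm the event falls in.

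**How often, and how the test behaves.** P(no event) = (1 − p)^N. The rejection rate comes from exact enumeration of all 2×2 tables, counting no-event trials as non-rejections. The ANOVA interval is the difference ± t(52 df) × √(MSE × (1/28 + 1/28)). Its coverage, given that it exists, is 1 − rejection/(1 − P(no event)); at 5%, 1 − 0.0250/0.9434 = 0.974.

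| Assumed rate | No event in 56 | No event in 200 | Condition test rejects | ANOVA interval coverage | ANOVA mean width (points) | Newcombe mean width (points) |
|---|---|---|---|---|---|---|
| 1% | 57% | 13% | 0.03% | 99.9% | 16 | 25 |
| 2% | 32% | 1.8% | 0.25% | 99.6% | 18 | 27 |
| 3% | 18% | 0.2% | 0.8% | 99.0% | 20 | 28 |
| 5% | 5.7% | <0.1% | 2.5% | 97.4% | 23 | 30 |
| 10% | 0.3% | <0.1% | 5.3% | 94.7% | 32 | 35 |

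All columns except the third are for 56 followed. The Newcombe widths average over all trials, including those without events, where the width is 2 × 12.1 = 24.2 points. That is below its average, so leaving those trials out would widen the gap. When rates were allowed to differ, simulated coverage of the ANOVA interval ran from 92.6% to 99.7%.

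So the planned analysis does not produce false signals with balanced cells: the test is conservative at 5% and below, and close to nominal at 10%.

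**What the alternative gives when F fails.** The Wilson upper limit for 0/28 is 3.84/(28 + 3.84) = 12.1%, so the Newcombe interval for 0/28 against 0/28 is ±12.1 points. For an event assumed to occur in 1% to 3%, that adds little to the bare statement that no event was reported.

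**What the alternative costs.** It reduces the planned gender factor to description and collapses any count or severity score to any/none. It also needs a denominator. Take 6-month completers, and suppose 80% complete each wave independently. Then 1 − 0.2³ = 99.2% return at least one survey, and 99.2% − 80% = 19.2% do so without the 6-month one. About 0.192/0.992 = 19% of those with any follow-up, and the events they reported, would be left out.

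**The case for a change.** The strongest case for the concern goes beyond the no-event trial. With zero or one event the F test carries no information on direction. That covers 89%, 69%, 50%, 22% and 2% of trials at rates of 1, 2, 3, 5 and 10% with 56 followed. Counts would still show where a single event fell, they cost a line of text, and an F test by itself is not an effect size. All of this is true. It supports adding counts; it does not show that the planned analysis misleads. A p-value of 0.32 from one event is an uninformative answer to uninformative data. Fitting the ANOVA also yields cell means, which for any/none scoring are the event proportions.

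The evidence for low rates is thin. The Section 6 remark concerns victimization only and gives no rate; nothing in the documents bears on how often perpetration is reported. Section 12 A describes suicidal and homicidal ideation and attempts, which "are possible given the high-risk nature of the population under study", so it does not settle SA frequency in either direction.

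Unequal gender groups can inflate the test. With 2% in the larger and 10% in the smaller gender, the interaction and Type III condition tests reject 13.8% of the time at 18/18/10/10. The effect needs an unusual split: 36/20 or worse in that direction has a 2.2% chance if each gender is equally likely. It falls to 5.2% at 17/17/11/11, reverses if the rates are reversed (0.45% to 1.3% over the splits examined), and is absent with Type II sums of squares (2.2% to 2.9%). It is not a reason to change the method.

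**Conclusion.** The concern does not hold. An undefined F is a real possibility, but it is common only at assumed rates of about 1% to 3% with 56 followed. It is uncommon at 5% (5.7%) and rare at 10% (0.3%); with 200 followed it is already down to 1.8% at a rate of 2%. These figures rest on rates, allocation and a gender split that the documents do not give. The test sizes and interval comparisons also assume any/none scoring.

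Where the ANOVA interval exists, it covers adequately under equal rates and is narrower than the Newcombe interval. Replacing it would be a debatable trade-off, not the correction of an error. No feasibility criterion uses these tests, and Section 10 bars efficacy conclusions from them, so no decision in this trial depends on the point. SA event counts by arm, with denominators, would help whoever plans the next trial. Nothing in the plan stands in the way of reporting them beside the ANOVA.
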